#### **4.2.2.1 Rationale for Use of Cisplatin + 5-Fluorouracil in First Line Gastric Cancer**

Systemic chemotherapy is the mainstay of treatment for advanced and metastatic gastric cancer and combination chemotherapy regimens containing cisplatin/5-fluorouracil (5-FU) for 1st line treatment have been investigated in the following randomized Phase 3 trials [32; 33].

The V325 trial [34] was the randomized Phase 3 study to compare docetaxel/cisplatin/5-FU with cisplatin/5-FU, and showed statistically significant OS time (median 9.2 months and 8.6 months, respectively,  $p = 0.02$ ) PFS time (median 5.6 months and 3.7 months, respectively,  $p = 0.001$ ), response rate (37% and 25%, respectively,  $p = 0.01$ ) associated with docetaxel/cisplatin/5-FU. Regarding the safety, the addition of docetaxel was associated with increased Grade 3-4 neutropenia (82%, versus 57% with 5 FU/cisplatin alone), complicated neutropenia (29% vs. 12%), Grade 3-4 diarrhoea (19% vs. 8%), and Grade 3-4 lethargy (19% vs. 14%). The result of V325 supported the registration of docetaxel and docetaxel/cisplatin/5-FU as one of the standard regimen for 1st line treatment for gastric cancer. However, due in part to this increased toxicity; incorporation of docetaxel into first-line gastric cancer regimens has been limited.

The Real-2 trial [35] was a phase 3 study to compare epirubicin + oxaliplatin + 5-FU [EOF], epirubicin + cisplatin + capecitabine [ECX], epirubicin + cisplatin + 5-FU [ECF], and epirubicin + oxaliplatin + capecitabine [EOX] in advanced esophagogastric cancer. OS was significantly longer among subjects receiving EOX versus ECF (9.9 months, 9.3 months, 9.9 months, and 11.2 months for ECF, EOF, ECX, and EOX, respectively). No significant differences were observed in terms of response rate or PFS. As an outcome of the Real-2 trial, cisplatin/5-FU/epirubicin became one of the popular regimens for 1st line treatment for gastric cancer in EU. However, according to the ESMO guideline (2013), the use of triplet regimen should be limited because of increased toxicity. There are no Phase 3 trials directly comparing cisplatin/5-FU and cisplatin/5-FU/epirubicin.

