**5.2.1.2.2 Dose Modification for Cisplatin and 5-FU**

Please refer to criteria for cisplatin and 5-FU (or capecitabine) dose modification included in [Table 7](#) and [Table 8](#), respectively.

Table 7 Dose Modification Guidelines for Cisplatin Drug-Related Adverse Events

Category	Toxicity	Hold Cisplatin Treatment for Grade	Timing for Restarting Cisplatin Treatment	Dose for Restarting Cisplatin Treatment	Discontinue Cisplatin
Haematologic 	Neutropenia	3 	Neutrophil count resolves to >1,000/mm 	No Reduction *consider G-CSF	Toxicity does not resolve within 4 weeks of last infusion or if >2 Dose Level reductions exceeded
		4 	Neutrophil count resolves to >1,000/mm 	Reduce by 1 DL *consider G-CSF	Toxicity does not resolve within 4 weeks of last infusion or if >2 Dose Level reductions exceeded
	Febrile Neutropenia	3 	Toxicity resolves to Grade 0-1	Reduce by 1 DL	Toxicity does not resolve within 4 weeks of last infusion or if >2 Dose Level reductions exceeded
		4 	n/a	Discontinue	Permanently discontinue Cisplatin
	Thrombocytopenia	3-4 	>75,000/mm  or baseline	Reduce by 1 DL	Toxicity does not resolve within 4 weeks of last infusion or if >2 Dose Level reductions exceeded

Category	Toxicity	Hold Cisplatin Treatment for Grade	Timing for Restarting Cisplatin Treatment	Dose for Restarting Cisplatin Treatment	Discontinue Cisplatin
Non-haematologic	Creatinine Increased	2	Toxicity resolves to Grade 0-1	Reduce by 1 DL	Toxicity does not resolve within 4 weeks of last infusion or if >2 Dose Level reductions exceeded
		3-4 	Toxicity resolves to Grade 0-1	Reduce by 1 DL	Toxicity does not resolve within 4 weeks of last infusion or if >2 Dose Level reductions exceeded
	Ototoxicity or Sensory neuropathy	3-4 	Toxicity resolves to Grade 0-1	Reduce by 1 DL	Toxicity does not resolve within 4 weeks of last infusion or if >2 Dose Level reductions exceeded
	All other non-haematologic toxicities 	3-4 	Toxicity resolves to Grade 0-1	Reduce by 1 DL	Toxicity does not resolve within 4 weeks of last infusion or if >2 Dose Level reductions exceeded
	Laboratory Adverse Events	4 	Toxicity resolves to Grade 0-1	Reduce by 1 DL	Toxicity does not resolve within 4 weeks of last infusion or if >2 Dose Level reductions exceeded

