- k. Pembrolizumab should be administered on Day 1 of each 3-week cycle after all procedures/assessments have been completed. Pembrolizumab 200 mg or placebo should be administered as a 30-minute IV infusion Q3W. Sites should make every effort to target infusion timing to be as close to 30 minutes as possible. However, given the variability of infusion pumps from site to site, a window of -5 minutes and +10 minutes is permitted (ie, infusion time is 30 minutes: -5 min/+10 min). For subjects randomized to the pembrolizumab/placebo plus cisplatin +5-FU arm, the pembrolizumab/placebo infusion is administered first followed by the cisplatin infusion and then 5-FU infusion.
- l. Cisplatin 80 mg/m^2 will be administered as a 60 or 120-minute IV infusion or per site's standard practice Q3W on Day 1 of each treatment cycle.
- m. 5-FU 800 mg/m^2/day will be administered as a continuous IV infusion from Day 1 to Day 5 (120 hours) of each treatment cycle. Although use of 5-FU infusion is preferred, Capecitabine 1000 mg/m^2 bid Day 1 to Day 14 Q3W may be permitted according to local guideline at Investigator decision. Decision regarding the type of comparator used (5-FU or capecitabine) should be determined prior to randomization in the trial.
- n. For women of reproductive potential, a serum pregnancy test should be performed within 72 hours prior to each cycle of trial treatment and 30 days post treatment. A urine test can be considered if serum is not appropriate. Pregnancy tests (serum and/or urine tests) should be repeated if required by local guidelines.
- o. Coagulation factors (PT/INR and aPTT) should be tested as part of the screening procedures for all subjects. And to be performed within 10 days prior to the first dose of trial treatment.
- p. ECOG PS for screening is to be performed within 3 days prior to the first dose of trial treatment. Laboratory tests for screening are to be performed within 10 days prior to the first dose of trial treatment. See Section 7.1.3 for details regarding laboratory tests. After Cycle 1, lab samples can be collected up to 72 hours prior to the scheduled time point. CBC with Differential, Chemistry panel, are to be repeated every 2 cycles after Cycle 6 (eg, Cycle 8-Day 1, Cycle 10-Day 1). Thyroid function

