tests should be collected every 6 weeks (every 2 cycles, eg, Cycles, 8, 10, 12, etc). Unresolved abnormal labs that are drug related AEs should be followed until resolution. Labs do not need to be repeated after the end of treatment if labs are within normal range.

- q. Serum CEA and CA 19-9 should be collected at screening (baseline), Cycle 3 and every 6 weeks (conducted at corresponding study visit; Cycle 5, Cycle 7, etc.) until study treatment discontinuation.
- r. This sample should be drawn for planned genetic analysis of DNA and drug response unless there is either a documented law or regulation prohibiting collection, or unless the IRB/IEC does not approve of the collection of the sample for these purposes. If the sample is collected, any leftover extracted DNA will be stored for future biomedical research if the subject signs the FBR consented. Detailed instructions for the collection and management of specimens are provided in the Procedures Manual and Section 12.2
- s. Whole blood sample for correlative studies should be collected at Cycle 1, Day 1- Pre-dose, Cycle 2 Day 1- Pre-dose, Cycle 3 Day 1 Pre-dose and again at treatment discontinuation. Blood for serum and blood for plasma to be collected only prior to the first dose of trial treatment. See Procedures Manual.
- t. Baseline tumour imaging will be performed within **21** days prior to randomization. Scans performed as part of routine clinical management are acceptable for use as the baseline scan if they are of diagnostic quality and performed within the allotted screening window for each cohort. The exact same image acquisition and processing parameters should be used throughout the study. The first on-study imaging time point will be performed 6 weeks ( $\pm 7$  days) after the subject has been randomized, or earlier if clinically indicated and will continue to be performed every 6 weeks ( $\pm 7$  days) until PD. Imaging timing should follow calendar days. On-study scans (scheduled and unscheduled) should be submitted to the central imaging vendor.

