## **7.0 TRIAL PROCEDURES**

### **7.1 Trial Procedures**

The Trial Flow Chart - Section 6.0 summarizes the trial procedures to be performed at each visit. Individual trial procedures are described in detail below. It may be necessary to perform these procedures at unscheduled time points if deemed clinically necessary by the investigator.

Furthermore, additional evaluations/testing may be deemed necessary by the investigator and or the Sponsor for reasons related to subject safety. In some cases, such evaluation/testing may be potentially sensitive in nature (e.g., HIV, Hepatitis C, etc.), and thus local regulations may require that additional informed consent be obtained from the subject. In these cases, such evaluations/testing will be performed in accordance with those regulations.

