#### **7.1.3 Laboratory Procedures/Assessments**

Details regarding specific laboratory procedures/assessments to be performed in this trial are provided below. The total amount of blood/tissue to be drawn/collected over the course of the trial (from pre-trial to post-trial visits), including approximate blood/tissue volumes drawn/collected by visit and by sample type per subject can be found in the Procedure Trial Procedures Manual. Refer to the TRIAL FLOW CHART (Section 6) for the timing of laboratory assessments.

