##### **7.1.3.1 Laboratory Safety Evaluations (Hematology, Chemistry and Urinalysis)**

Laboratory tests for hematology, chemistry and urinalysis are specified in [Table 10](#).

Table 10 Laboratory Tests

Hematology	Chemistry	Urinalysis	Other
Hematocrit	Albumin	Blood	Serum $\beta$ -human chorionic gonadotropin ( $\beta$ -hCG) c
Hemoglobin	Alkaline phosphatase	Glucose	PT (INR)
Platelet count	Alanine aminotransferase (ALT)	Protein	aPTT
WBC (total and differential) a	Aspartate aminotransferase (AST)	Specific gravity	Total triiodothyronine (T3) or Free T3
Absolute Neutrophil Count	Carbon dioxide (CO 2 or bicarbonate) b	Microscopic exam, if abnormal results are noted	Free thyroxine (T4)
Absolute Lymphocyte Count	Calcium	Urine pregnancy test c	Thyroid stimulating hormone (TSH)
	Chloride		
	Creatinine		
	Glucose		
	Magnesium		
	Phosphorus		
	Potassium		
	Sodium		
	Total Bilirubin		
	Direct Bilirubin, if total bilirubin is elevated above the upper limit of normal		
	Total protein		
	Blood Urea Nitrogen/Urea d		
	Uric acid		

a. Absolute or % is acceptable.  
b. If these tests are not done as part of standard of care in your region then these tests do not need to be performed.  
c. Perform on women of childbearing potential only. Serum pregnancy test is preferred but urine test can be considered if serum not appropriate.  
d. Blood Urea Nitrogen is preferred; if not available urea may be tested.

Laboratory tests for screening should be performed within 10 days prior to the first dose of trial treatment. An exception is hepatitis and thyroid serologies, which may be performed within 28 days prior to first dose. Subjects eligible for trial retreatment should have imaging performed within 21 days and laboratory tests performed within 7 days prior to the first dose

of trial treatment in the Second Course Phase. After Cycle 1, in both the Initial Treatment Phase and the Second Course Phase, pre-dose laboratory safety tests can be conducted up to 72 hours prior to dosing unless otherwise noted on the flow charts.

Laboratory test results must be reviewed by the investigator or qualified designee and found to be acceptable prior to administration of each dose of trial treatment.

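### After Cycle 6, the Arms 2 and 3 flow chart schedules blood counts and chemistry every second cycle while chemotherapy is given every cycle, in conflict with the per-dose review rule in 7.1.3.1

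*Combined protocol and SAP*

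**What the plan says.** **Test schedule.** In the Arms 2 and 3 chart (6.1.2), CBC and chemistry are marked at screening, at Cycles 2 to 5, and in the column for Cycle 6 onward. Footnote p, attached to both rows, thins the later draws: "CBC with Differential, Chemistry panel, are to be repeated every 2 cycles after Cycle 6 (eg, Cycle 8-Day 1, Cycle 10-Day 1").

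**Dosing schedule.** The same chart marks pembrolizumab/placebo, cisplatin and the fluoropyrimidine at every cycle. Footnote m says that 5-FU "will be administered as a continuous IV infusion from Day 1 to Day 5 (120 hours) of each treatment cycle"; capecitabine is also given every 3 weeks. Table 3 (5.2) lets cisplatin stop at 6 cycles where local country guidelines say so, but the fluoropyrimidine may go on. Section 5.2.3 sets the limit at 35 administrations.

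**Review rule.** Section 7.1.3.1 says that laboratory results must be "reviewed by the investigator or qualified designee and found to be acceptable prior to administration of each dose of trial treatment". For timing, 7.1.3 says: "Refer to the TRIAL FLOW CHART (Section 6) for the timing of laboratory assessments".

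**Holds.** Tables 7 and 8 (5.2.1.2.2) hold chemotherapy for Grade 3-4 neutropenia and thrombocytopenia. Table 7 also has a row for "Creatinine Increased", which holds cisplatin from Grade 2.

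**Other provisions.** Section 7.1 adds: "It may be necessary to perform these procedures at unscheduled time points if deemed clinically necessary by the investigator". Footnote p adds: "Unresolved abnormal labs that are drug related AEs should be followed until resolution". Adverse event review, directed examination and vital signs continue at every cycle.

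**The concern.** A hold based on a neutrophil count, platelet count or creatinine works only if a current value exists when the dosing decision is made. A site that follows the chart exactly has no such value at Cycles 7, 9, 11 and so on. The Cycle 6 sample is taken before the Cycle 6 chemotherapy, so it cannot show what that chemotherapy did. A new abnormality without symptoms could then go unseen before the next dose. The same site would also be unable to show that it had met 7.1.3.1 in any useful sense.

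What is at stake is the safety of subjects on prolonged chemotherapy in Arms 2 and 3, and a protocol that gives sites two different instructions. No efficacy endpoint or analysis is affected.

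**Working it through.** **1. Compare the two schedules.**

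| Cycles | Chemotherapy dose | Scheduled CBC and chemistry before it |
|---|---|---|
| 1 | yes | yes (screening tests, within 10 days) |
| 2 to 6 | yes | yes, each cycle |
| 8, 10, ..., 34 | yes | yes |
| 7, 9, ..., 35 | yes | none |

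Cycles after Cycle 6: 35 − 6 = 29. Cycles without a scheduled result: (35 − 7)/2 + 1 = 15. Scheduled draws are 2 × 21 = 42 days apart and doses 21 days apart. At each odd cycle the last scheduled result is therefore about 3 weeks old, with one chemotherapy dose given since.

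**2. Does the chart qualify the review rule?** Section 7.1.3.1 does defer to the flow charts in one place, but that exception belongs to the sentence that allows pre-dose samples up to 72 hours before dosing. The review rule is a separate paragraph without an exception.

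**3. Does any other provision schedule the missing test?**
- Unscheduled testing under 7.1 is at the investigator's discretion.
- Follow-up of unresolved abnormalities under footnote p covers abnormalities already known.
- Adverse event review, examination and vital signs do not measure a count or creatinine.
- The tumour markers CEA and CA19-9 (footnote q) and pregnancy tests (footnote n) are scheduled at odd cycles, but they do not inform the holds in question.

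None of these requires a CBC or chemistry test at the odd cycles.

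**4. Can the number of affected doses be estimated?** Only as an illustration. Inputs from 8.9: exponential PFS with a control median of 6 months, hazard ratio 0.65 (combination median 6/0.65 = 9.23 months), 5% yearly dropout, and 250 subjects per arm (750/3).

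Day 1 of Cycle k falls at t = 21(k − 1)/30.44 months. The share progression-free and on study is P = exp(−ln 2 × t/median) × 0.95^(t/12).

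- Cycle 7: t = 126/30.44 = 4.14 months. P = 0.609 (control) and 0.720 (combination). 250 × 0.609 + 250 × 0.720 = 152 + 180 = 332 of 500 subjects.
- Sum of 250 × P over the 15 odd cycles: 915.5 + 1,399.5 = 2,315 dosing cycles if nobody stops chemotherapy before progression, or 2,315/332 = 7.0 per subject reaching Cycle 7.

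The plan gives no chemotherapy stopping rate. With an assumed constant rate s per cycle, each term is multiplied by (1 − s)^(k − 7) if stopping starts after Cycle 7, or by (1 − s)^(k − 1) if it starts after Cycle 1:

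| Assumed s | Stopping from Cycle 7 | Stopping from Cycle 1 |
|---|---|---|
| 5% | 1,539 | 1,131 |
| 10% | 1,136 | 603 |
| 20% | 755 | 198 |

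The count therefore runs from about 200 to about 1,500 across these assumptions. Nor is 2,315 a ceiling, because 2.1 lets clinically stable subjects continue treatment after progression on imaging.

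**The case against.** The strongest reply is that 7.1.3.1 already protects subjects. If acceptable results are mandatory before each dose, a careful site will draw blood at Cycle 7 whatever footnote p says, and the defect is only an unclear footnote. If instead the rule can be met by looking again at the last available result, there is no strict conflict, only a choice of monitoring frequency.

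Part of this stands. 7.1.3.1 does not itself order a new sample, and a site that reads it strictly will close the gap, so practical risk is lower than the chart alone suggests. But neither reading rescues the text. On the strict reading, the chart that 7.1.3 makes the authority on timing omits tests that the rule needs. On the lenient reading, the review uses values from before the previous chemotherapy dose and cannot detect new toxicity.

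Two further points stand. Subjects reaching Cycle 7 have had counts before Cycles 2 to 6, with holds and dose reductions as needed, and some will be off cisplatin. Anyone already held needs documented recovery to restart, so the gap concerns new abnormalities only. Also, the review rule covers every dose of trial treatment. Subjects continuing on pembrolizumab alone, as 5.2.1.2 allows, would remain in conflict with 7.1.3.1 if only the chemotherapy cycles were corrected.

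A reader might also infer from 4.2.2.1 that silent neutropenia is common at these visits, since it reports "Grade 3-4 neutropenia (82%, versus 57% with 5 FU/cisplatin alone), complicated neutropenia (29% vs. 12"%). On cisplatin/5-FU alone that leaves (57 − 12)/57 = 79% not complicated, if complicated cases are a subset. The documents do not support the inference. The term complicated is not defined there, not complicated does not mean without symptoms, and the figures come from another trial and are not specific to Day 1 of later cycles.

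**Conclusion.** The point holds as a mismatch in the text with a safety consequence. At up to 15 of the 29 cycles from 7 to 35, chemotherapy may be given in Arms 2 and 3 with no scheduled CBC or chemistry result that postdates the previous chemotherapy dose. That conflicts with 7.1.3.1 and leaves the neutrophil, platelet and (Table 7 only) creatinine holds without a scheduled trigger for new toxicity. This rests only on the chart, footnotes m and p, 5.2.3, 7.1.3 and 7.1.3.1, and needs no assumed rate. Fifteen is the maximum, for a subject on chemotherapy through Cycle 35.

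A count of harmful doses is not supported. A reader might multiply the affected cycles by an assumed 1% to 5% prevalence of new silent Grade 3-4 counts and get anything from 198 × 1% = 2 to 2,315 × 5% = 116. Both factors are assumptions, and the range shows that the plan cannot settle the size of the harm. The sponsor should make the change because a schedule followed exactly permits dosing on outdated values and the correction is small.

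**What to change.** 1. In 6.1.2, footnote p, require CBC with differential and the chemistry panel within 72 hours before Day 1 of every cycle in which cisplatin, 5-FU or capecitabine is given, with results reviewed before dosing.
2. In the same footnote, keep testing every 2 cycles after Cycle 6 for subjects no longer on chemotherapy.
3. In 7.1.3.1, state that for cycles without chemotherapy the most recent scheduled result is the one reviewed. This removes the remaining conflict for subjects on pembrolizumab alone. As a general statement, it also covers Arm 1 (6.1.1, footnote n) and the Second Course Phase (6.2, footnote k), whose charts carry the same schedule.

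Scheduled draws during chemotherapy would then be 3 weeks apart instead of 6, and chemotherapy cycles without a scheduled result would fall from up to 15 to 0. The cost is two short text changes and added local CBC and chemistry tests. The odd-cycle visits already exist for dosing, and footnote q already schedules a CEA and CA19-9 sample at them, so the change should usually need no extra visit or venipuncture.
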